1. Study Title

Association of the $\text{PaO}_2/\text{PaCO}_2$ Ratio With ICU Mortality Independent of Oxygen Saturation and Mean Arterial Pressure: A MIMIC-II Retrospective Cohort Study

Acronym: RATIO-MIMIC

2. Study Objectives

Primary Objective:

- To determine whether the $\text{PaO}_2/\text{PaCO}_2$ ratio is independently associated with ICU mortality in critically ill adults, adjusting for oxygen saturation (SpO_2) and mean arterial pressure (MAP).

Secondary Objectives:

- To explore the relationship between $\text{PaO}_2/\text{PaCO}_2$ ratio categories (e.g., tertiles or quartiles) and ICU length of stay.
- To perform subgroup analyses by mechanical ventilation status, age, or primary ICU diagnosis.

3. Study Design

- **Type:** Observational
- **Design:** Retrospective cohort study
- **Population:** Adult ICU patients (≥ 18 years) in MIMIC-II database
- **Sampling Method:** Retrospective census of all eligible patients meeting inclusion/exclusion criteria
- **Cohorts/Groups:** Single cohort; exposure analyzed as continuous and categorical (quartiles or tertiles)
- **Time Frame:** ICU admissions from 2001–2008 (MIMIC-II database)

4. Study Population

Inclusion Criteria:

1. Adult patients (≥ 18 years) at ICU admission
2. First (index) ICU admission during hospitalization

3. At least one arterial blood gas measurement with PaO_2 and PaCO_2
4. Available SpO_2 and MAP during ICU stay
5. Documented ICU discharge status

- **Exclusion Criteria:**
 1. Age <18 years
 2. Missing or non-numeric PaO_2 or PaCO_2 values
 3. Missing ICU outcome data
 4. Physiologically implausible ABG values
 5. ECMO during ABG measurement (if identifiable)
 6. No SpO_2 or MAP measurements during ICU stay
 7. Repeat ICU admissions beyond index stay
 8. DNR/comfort-care orders prior to ABG measurement (optional for sensitivity analyses)

5. Data Collection and Variables

- **Exposure Variable:** $\text{PaO}_2/\text{PaCO}_2$ ratio (calculated from ABG measurements)
- **Outcome Variable:** ICU mortality (yes/no)
- **Covariates for Adjustment:**
 - Oxygen saturation (SpO_2)
 - Mean arterial pressure (MAP)
 - Age, sex, ICU type (medical/surgical), comorbidities (if available)
 - Mechanical ventilation status
- **Time Points:** First ABG per ICU stay (primary), or median/peak ABG values for sensitivity analysis

6. Statistical Analysis Plan (SAP)

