6.2 Primary Analysis

- **Model:** Multivariable logistic regression
- **Dependent Variable:** ICU mortality (binary)
- **Independent Variable:** $\text{PaO}_2/\text{PaCO}_2$ ratio (continuous or categorical)
- **Covariates:** SpO_2 , MAP, age, sex, ICU type, comorbidities
- **Effect Measures:** Adjusted odds ratios (ORs) with 95% confidence intervals
- **Assessment of Independence:** Evaluate whether $\text{PaO}_2/\text{PaCO}_2$ remains statistically significant after adjustment

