6.5 Statistical Software

- R (version ≥ 4.0) or STATA (version ≥ 16)
- Two-sided p-value <0.05 considered statistically significant

7. Ethical Considerations

- Secondary analysis of **de-identified public data (MIMIC-II)**
- No new patient consent required
- Approved by MIT and Beth Israel Deaconess Medical Center Institutional Review Boards for public data use

8. Reporting

- Follow **STROBE guidelines** for observational studies
- Present baseline tables, regression results, and flowchart of included/excluded patients
- Include sensitivity and subgroup analyses
- Report odds ratios, 95% CI, and p-values

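### SpO2 and MAP are the only acute-physiology terms in the primary model, so a significant ratio can reflect residual acute severity rather than an independent association

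*Combined protocol and SAP*

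**What the plan says.** The primary objective (Section 2) asks whether the ratio "is independently associated with ICU mortality in critically ill adults", and the same sentence goes on to name adjustment for SpO2 and MAP. The title also ties independence to those two variables.

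The primary analysis (Section 6.2) is "Multivariable logistic regression" of ICU death on the ratio, continuous or categorical. Its covariates are SpO2 and "MAP, age, sex, ICU type, comorbidities". Independence is assessed by whether the ratio "remains statistically significant after adjustment", and Section 6.5 sets the threshold: "Two-sided p-value <0.05 considered statistically significant".

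Section 5 gives the same adjustment list, with comorbidities conditional on availability and ICU type defined as medical or surgical. It adds mechanical ventilation status, which is not in the 6.2 model. Section 2 plans subgroups by "mechanical ventilation status", age or primary ICU diagnosis; Section 6.3 lists ventilation, age categories and ICU type.

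The sensitivity analyses in 6.3 vary the handling of extreme blood gases, DNR/comfort-care patients and first versus median blood gas. The missing-data rule for covariates in 6.4 names SpO2, MAP and comorbidities.

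**The concern.** In the 6.2 model every covariate other than SpO2 and MAP is demographic, unit-level or chronic. A consciousness score, a renal, hepatic or coagulation measure, and a composite severity score are absent from every covariate list, subgroup and sensitivity analysis.

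Some of these states plausibly affect both the exposure and the outcome. PaCO2 depends on ventilation. Respiratory depression in coma raises PaCO2 and lowers the ratio; hyperventilation in acute brain failure, or in compensation for a metabolic acidosis that accompanies renal or hepatic failure, lowers PaCO2 and raises it. The same states raise the risk of death. Comorbidity describes chronic disease and ICU type separates units, so neither captures how acutely ill a patient is within a unit.

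At stake is the only primary conclusion. It depends on one significance test, whose meaning depends on the covariate set. If acute severity is left out, a significant adjusted OR cannot be told apart from severity of illness, and nothing in 6.3 would reveal this.

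**Working it through.** The documents give no sample size, event count or effect size, so there is no figure of theirs to reproduce. Two illustrations follow; all their numerical inputs are assumptions.

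**1. Closed form: one omitted binary organ failure**

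Inputs: true OR for the ratio 1.0; mortality without the failure 8%; the failure multiplies the odds of death by k = 2, 3, 4 or 6; prevalence p1 in the top quartile and p0 in the bottom. These prevalences must be read as the imbalance that remains after adjustment for the 6.2 covariates; the calculation itself contains none.

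- Risk with the failure: odds = k × 0.08/0.92, risk = odds/(1 + odds).
- Quartile risk: R = (1 − p) × 0.08 + p × (risk with failure).
- Spurious OR = [R1/(1 − R1)] / [R0/(1 − R0)].

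Worked case, k = 3, 20% versus 10%: odds 0.2609, risk 0.2069. R1 = 0.8 × 0.08 + 0.2 × 0.2069 = 0.1054. R0 = 0.9 × 0.08 + 0.1 × 0.2069 = 0.0927. OR = 0.1178/0.1022 = 1.15.

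| p1 vs p0 | k = 2 | k = 3 | k = 4 | k = 6 |
|---|---|---|---|---|
| 20% vs 10% | 1.09 | 1.15 | 1.21 | 1.29 |
| 30% vs 20% | 1.08 | 1.14 | 1.18 | 1.24 |
| 30% vs 15% | 1.13 | 1.22 | 1.29 | 1.39 |
| 40% vs 20% | 1.16 | 1.28 | 1.36 | 1.49 |

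For k from 2 to 4 the range is 1.08 to 1.36. All entries exceed 1 only because the failure was placed in the top quartile. Swapping the quartiles gives the reciprocals, for example 1/1.15 = 0.87 and 1/1.36 = 0.74.

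**2. Simulation: a continuous severity score left out of a 6.2-type model**

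Inputs: true OR 1; mortality 10%; three measured covariates; correlation of the ratio with the omitted score, given those covariates, of −0.1 or −0.2; OR for death per SD of the score 1.5 or 2.0; 400 replicates per setting (200 at N = 10,000).

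| N | Spurious OR per SD of ratio | Declared significant |
|---|---|---|
| 1,000 | 0.87–0.95 | 7%–24% |
| 5,000 | 0.88–0.96 | 14%–79% |
| 10,000 | 0.88–0.96 | 20%–99% |

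Two further settings, both at N = 5,000 and OR 2.0 for the score:

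- Correlation +0.1: OR 1.07, significant in 31%.
- Correlation zero: OR 1.00, significant in 3.5%. There is no bias unless the ratio and the omitted severity are linked beyond the measured covariates.

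With the score in the model, the OR is 0.99 to 1.00 in all 14 settings. Rejection ranges from 2.0% to 8.5% and averages 4.8%. One standard error at 400 replicates is √(0.05 × 0.95/400) = 1.1 points, so the single 8.5% is on the high side, but the average is nominal.

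Section 3 plans a census judged on significance. For a fixed bias, the chance of a false finding therefore rises with the size of the cohort.

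**The case against.** The strongest reply is that the question is narrower than the criticism. The title and the full sentence of the objective define independence relative to SpO2 and MAP, and the model includes both. This has force: the plan does not promise independence from all severity of illness. It does not settle the matter, because 6.2 already adjusts for age, sex, ICU type and comorbidities, and so accepts that confounding beyond SpO2 and MAP needs control. Its independence criterion is also stated without that qualifier. If the narrow claim is intended, the conclusion should be worded that way.

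A second reply is that ventilation status, in the Section 5 list and a subgroup in 6.3, is acute and would absorb part of the coma example. That is fair, but 6.2 does not include it, and it does not measure renal, hepatic or coagulation failure. The diagnosis subgroups in Section 2 likewise help only in part.

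Third, the mechanisms act in opposite directions and could partly cancel, the route from coagulation failure to the ratio is the least direct, and the closed form is crude. All of this stands. It limits what can be said about size and sign, but gives no reason to assume that the bias is nil.

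**Conclusion.** The point stands in a limited form. As written, 6.2 can credit residual acute severity to the ratio, and no other analysis in the plan would detect it. The spurious top-versus-bottom OR of about 1.1 to 1.4 is illustrative. It assumes a true OR of 1, 8% base mortality, a failure that multiplies the odds of death by 2 to 4, and prevalence imbalances that survive adjustment for the listed covariates. With the imbalance reversed, the OR falls below 1 by the reciprocal factor.

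A reader might infer that the ratio will be wrongly declared an independent predictor, or that the bias inflates its OR. The documents support neither. They give no data on the link between the ratio and organ failure given the listed covariates, and without such a link there is no bias. A reader might also infer that the plan ignores acute state altogether apart from SpO2 and MAP. It does not: Section 5 names mechanical ventilation as an adjustment covariate, although 6.2 omits it.

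**What to change.** 1. Reconcile 6.2 with Section 5 on mechanical ventilation, so that there is one adjustment list.
2. Pre-specify in 6.2 non-respiratory acute-severity covariates: a consciousness score with renal, hepatic and coagulation items. Alternatively, use one severity score with all PaO2, PaCO2, oxygenation, ventilation and MAP components removed, so that neither the exposure nor SpO2 and MAP enter twice. Age or comorbidity items in such a score must not duplicate existing covariates.
3. Use values recorded at or before the index blood gas, so that the model does not adjust for consequences of the exposure. Add these variables to the covariates covered by 6.4. Availability in the database is an assumption; drop any item it does not hold.
4. Keep the present 6.2 set as a sensitivity model, and word the conclusion as association after adjustment for the listed covariates.

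A lighter alternative is a severity-adjusted sensitivity analysis with an E-value and the same limit on wording. It is defensible if the narrow question is the intended one, but it leaves the primary estimate exposed.

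The cost is SAP wording and further extraction, with no new patients. Laboratory values before a first blood gas may often be missing and need imputation; the documents do not show how often. Consciousness scores are less reliable under sedation. The change should be made before the outcome analysis, because adding severity terms afterwards would look selective.

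### Section 6.2 states no functional form for SpO2; if it is entered as a straight line, curvature in the SpO2-mortality relation can make the ratio look independent when it is not

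*Combined protocol and SAP*

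**What the plan says.** Section 2 sets the primary objective as an association with ICU mortality, "adjusting for oxygen saturation (SpO_2) and mean arterial pressure (MAP" (the quote stops before the closing bracket). Section 6.2 names the model, "Multivariable logistic regression", and lists the covariates: SpO2, followed by "MAP, age, sex, ICU type, comorbidities". No linear term, spline, category, polynomial or linearity check is mentioned for any continuous covariate. The form of the exposure is also left open: "ratio (continuous or categorical".

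The test of independence in 6.2 is whether the ratio "remains statistically significant after adjustment", and 6.5 sets the threshold: "Two-sided p-value <0.05 considered statistically significant". The sensitivity analyses in 6.3 vary the handling of extreme blood gases, of DNR or comfort-care patients, and of first versus median blood gas. None varies the form of a covariate.

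Two other entries matter. Section 3 gives no sample size and describes a "Retrospective census of all eligible patients meeting inclusion/exclusion criteria". Section 4 requires only "Available SpO_2 and MAP during ICU stay", with no link in time to the first blood gas.

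**The concern.** A claim of independence from SpO2 is only as good as the adjustment for SpO2. A bare covariate list in a logistic model is usually fitted as one linear term per variable, which forces log-odds of death to change by the same amount per saturation point everywhere.

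SpO2 is not an ordinary covariate here. Saturation is a sigmoid function of PaO2, and PaO2 is the numerator of the exposure. If the true SpO2-mortality relation bends, the part the straight line misses is correlated with the ratio, and the ratio can take it up. The ratio would then stay significant because SpO2 was under-adjusted, which is the explanation the primary objective is meant to exclude. Nothing in 6.3 would reveal it.

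**Working it through.** **Inputs from the documents.** Logistic model, covariate list, significance as the criterion, two-sided 0.05. The documents state no sample size, mortality, event count or effect size, so there is no figure of the plan's own to reproduce. The check is a simulation in which the ratio has no effect.

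**Assumptions (none from the documents).** PaO2 log-normal, median 110, log-SD 0.5. PaCO2 log-normal, median 41, log-SD 0.22. SpO2 = 100/(23400/(PaO2³ + 150·PaO2) + 1) plus noise of SD 1.5, capped at 100. Mortality 12%. True model: logit P(death) = a + f(SpO2) + 0.02(age − 63) − 0.015(MAP − 78). There were 300 runs per cell (200 at N=10,000). The Monte Carlo SE at 5% is √(0.05·0.95/300) = 1.3 points, or 1.5 points with 200 runs. The ratio entered as a continuous variable; its categorical form was not simulated.

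**The link between ratio and SpO2.** From the formula, before noise and with PaCO2 at 41:

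- PaO2 60: SpO2 90.6, ratio 1.46
- PaO2 110: SpO2 98.3, ratio 2.68
- PaO2 200: SpO2 99.7, ratio 4.88

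The first step adds 7.7 saturation points and 1.22 to the ratio. The second adds 1.4 points and 2.20. The simulated ratio-SpO2 correlation was 0.49.

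**False-positive rate for the ratio, N = 1,000 / 5,000 / 10,000.**

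| Assumed f(SpO2), log-odds per point | Linear SpO2 term | OR per SD of ratio, linear term | Spline for SpO2 |
|---|---|---|---|
| Linear, −0.08 | 4.7 / 5.0 / 5.5% | 0.98-1.00 | 3.7 / 4.7 / 6.0% |
| Threshold: 0.10 below 92, flat above | 12.3 / 41.0 / 73.0% | 1.09 | 4.7 / 5.0 / 4.0% |
| Weak U: 0.08 below 96, 0.05 above | 13.0 / 39.7 / 64.5% | 1.08-1.09 | 2.7 / 7.3 / 4.5% |
| Middle U: 0.08 below, 0.10 above | 14.0 / 57.0 / 86.0% | 1.09-1.11 | 6.7 / 8.7 / 6.0% |
| Strong U: 0.10 below, 0.20 above | 32.3 / 94.3 / 100% | 1.17-1.19 | 6.0 / 5.3 / 4.0% |

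With the spline the mean OR was 0.97-1.00. The highest spline cell, 8.7%, lies (8.7 − 5)/1.26 = 2.9 SE above 5%, but the same shape gave 6.0% at N=10,000, whereas a bias would grow with N.

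**Why N matters.** The spurious OR hardly changes with N while its standard error shrinks. In the threshold row, 41% at N=5,000 implies a mean z of 1.96 − 0.23 = 1.73. At N=10,000 this becomes 1.73·√2 = 2.45, predicting Φ(0.49) = 69% (simulated 73%, SE about 3). At N=1,000 it becomes 1.73/√5 = 0.77, predicting about 12% (simulated 12.3%).

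**Other assumed inputs.** A separate null simulation at N=5,000 (120 runs) gave 62% for a moderate U and 63% for a low-saturation threshold with a linear term, against 6% and 3% with a four-knot spline, and 3-4% with either form when the truth was linear. Slopes of 0.15 to 0.30 per point above 96 gave 73-100% at N=5,000 and 99-100% at N=15,000, against 4-10% with splines. Low-saturation-only risk depends on the shape: 0.15 per point below 92 gave 77% at N=5,000, while another assumed shape gave only 2-6%.

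**MAP.** With U-shaped MAP risk and a linear MAP term at N=5,000, the rate was 5.3% if MAP was independent of the ratio, 6.0% if linearly correlated at −0.2, and 21% only if the ratio was lower at both MAP extremes.

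**SpO2 not time-matched to the blood gas.** With a truly linear SpO2 effect, N=5,000 and mismatch noise of SD 2-3 points (assumed), the rate was 11-30% with a linear term and 23-48% with a four-knot spline. Another such run gave 7% and 17%. With mismatch and a U-shape it was 35-52% linear and 8-11% spline.

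**The case against.** The strongest reply is that the plan never says linear. Splines, categories or a linearity check would all be consistent with 6.2. That is correct: the defect is an unspecified form, and linear entry is an inference from usual practice. It does not remove the problem, because an open form can also be chosen after the results are seen, and the primary conclusion turns on it.

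Second, a reader might infer that a U-shaped SpO2-mortality relation is established and that the plan will therefore produce false independence. The documents describe no shape. The turning point at 96 and all the slopes are assumptions, and under a linear truth nothing leaks. Nor is a U needed, since a threshold can do the same. It would be equally unsafe to infer that linear terms are adequate whenever risk rises only at low saturation, because that held for one assumed shape and failed for others.

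Third, since the objective names SpO2 and MAP together, a reader might extend the mechanism to MAP. The sigmoid link to PaO2 does not apply to MAP, and the rate stayed near nominal unless the ratio itself was curved in MAP. For age nothing was tested.

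Fourth, the spline is not a full safeguard. With SpO2 mistimed and truly linear, it did worse than the straight line. This objection stands in full.

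Fifth, four knots at percentiles is one acceptable choice among several. That also stands; what matters is that a flexible form is fixed in advance.

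**Conclusion.** The concern holds in a conditional form. Section 6.2 does not fix the form of SpO2, the covariate most closely tied to the exposure, and judges independence by significance alone. If SpO2 is entered linearly and its true relation to mortality is curved, the ratio can be significant with no effect of its own. In the curved shapes tabulated, the false-positive rate was about 12% to 100%, with spurious ORs of about 1.08 to 1.19 per SD of the ratio. Across all the simulations without mistiming, a spline gave about 3-10%.

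These sizes rest on assumed distributions, shapes, mortality and sample sizes, and they show what can happen, not what will. The documents do not support the stronger conclusions that the planned analysis is linear, that false independence is the expected result, or that MAP carries the same risk. The change should be made because it is cheap and protects the primary conclusion. It does not by itself secure a claim of independence.

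**What to change.** State in 6.2 that SpO2 enters the primary model as a restricted cubic spline, for example with four knots at fixed percentiles, and that the primary conclusion rests on that model. Apply the same form to MAP and age as good practice. Add the linear-term model to 6.3 as a sensitivity analysis and report the ratio's odds ratio from both models side by side. Because SpO2 piles up near its ceiling (in the simulated cohort the 75th percentile was 99.5 and the 95th was 100), say what is done if upper knots coincide.

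A four-knot restricted cubic spline uses three parameters instead of one, so the cost is two extra degrees of freedom per variable, or six for all three. No new data are needed.

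The text should also say that the spline addresses curvature only. Which SpO2 value is used, and how close in time it must be to the first blood gas, has to be defined separately, since a spline does not remove confounding left by mistimed readings.

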6.3 Secondary Analyses

- **Subgroup Analyses:** Mechanical ventilation status, age categories, ICU type
- **Sensitivity Analyses:**
 - Excluding extreme ABG values
 - Excluding DNR/comfort-care patients
 - Using alternative $\text{PaO}_2/\text{PaCO}_2$ calculation methods (first ABG vs. median ABG)
- **Time-to-event Analysis (Optional):** Cox proportional hazards for ICU length of stay, treating death as event

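### Patients with a single blood gas have identical first and median values, so the whole-cohort first-versus-median check in 6.3 is diluted toward agreement by an unreported amount

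*Combined protocol and SAP*

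**What the plan says.** Inclusion criterion 3 in section 4 asks for "At least one arterial blood gas measurement with PaO_2 and PaCO_2", so a patient with exactly one gas is eligible. Section 5 sets the time points as "First ABG per ICU stay (primary), or median/peak ABG values for sensitivity analysis". Section 6.3 then lists the comparison "first ABG vs. median ABG" among the sensitivity analyses. It is the only item there that varies which gas supplies the exposure.

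The plan does not limit this comparison to patients with two or more gases, does not stratify by number of gases, and does not ask for that number to be reported. It sets no criterion for calling a result robust. The one decision rule is in 6.2, where the ratio is judged by whether it "remains statistically significant after adjustment", with the threshold in 6.5 ("Two-sided p-value <0.05 considered statistically significant"). The effect measure is "Adjusted odds ratios (ORs) with 95% confidence intervals". No sample size, event count or single-gas share is stated. The sampling frame is a census of eligible patients.

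**The concern.** A sensitivity analysis is informative to the extent that it could have come out differently. For a patient with one gas, the first, the median and the peak are the same value, so that patient contributes the same exposure and outcome to both fits. Such patients pull the median-based estimate toward the first-gas estimate whatever happens in the patients whose gases vary.

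What is at stake is a sentence in the eventual report. If the two ORs look similar, the authors may write that the finding does not depend on the choice of gas. Part of that similarity would be built in, and without the gas counts a reader could not tell how much.

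**Working it through.** There is no figure in the plan to reproduce, so the check is an identity followed by a range of assumed scenarios.

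**Identity.** With one gas, first = median = peak. Section 4 admits such patients, and 6.3 does not remove them.

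**Approximation.** If single-gas patients carry a share *w* of the statistical information, then

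log OR (median, whole cohort) ≈ *w* × *b*₁ + (1 − *w*) × *b*ₘ,

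where *b*₁ is the first-gas log OR (the same in everyone) and *b*ₘ is the median log OR in patients with two or more gases. With exposure on a common SD scale and equal mortality, *w* equals the head-count share *s*. With unequal mortality, each group is weighted by p(1 − p).

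**Assumed inputs (none from the documents).** *s* = 20%, 30%, 50%, 70%; *b*₁ = 0.20 (OR 1.22 per SD); five gases per multi-gas patient with within-patient correlation 0.5, giving a first-to-median correlation of about 0.75.

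- *Extreme case, equal mortality of 10%:* *b*ₘ = 0, *w* = *s*, OR = exp(0.20*s*).
- *Extreme case, mortality 4% (single) and 12% (multiple):* *w* = 0.0384*s* / [0.0384*s* + 0.1056(1 − *s*)], using 0.04 × 0.96 and 0.12 × 0.88. This gives *w* = 0.083, 0.135, 0.267 and 0.459; OR = exp(0.20*w*).
- *Milder case, only the first gas matters, equal mortality:* *b*ₘ = 0.75 × 0.20 = 0.15 (OR 1.16), OR = exp(0.20*s* + 0.15(1 − *s*)).

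| Single-gas share | Extreme, equal mortality | Extreme, 4% and 12% | Milder case | Milder: excess over 1.16 |
|---|---|---|---|---|
| 20% | 1.04 | 1.02 | 1.17 | 0.01 |
| 30% | 1.06 | 1.03 | 1.18 | 0.02 |
| 50% | 1.11 | 1.05 | 1.19 | 0.03 |
| 70% | 1.15 | 1.10 | 1.20 | 0.04 |

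Simulated logistic fits agree closely: about 1.04 to 1.15, about 1.01 to 1.10, and a milder-case distortion of about 0.01 to 0.05. In the extreme case, fits in multi-gas patients alone returned a median OR of about 1.00.

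**Effect on a significance reading.** A second simulation used a first-gas OR of 0.80 per SD, a median OR of 1.00 in multi-gas patients, unadjusted models and 300 replicates per setting. The table gives the percentage of replicates in which the whole-cohort median analysis was significant in the same direction as the first-gas association.

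| Single-gas share | N = 10,000, 10% both | N = 3,000, 10% both | N = 10,000, 4% and 12% | N = 3,000, 4% and 12% |
|---|---|---|---|---|
| 10% | 11 | 7 | 4 | 4 |
| 20% | 41 | 16 | 12 | 4 |
| 30% | 72 | 27 | 17 | 7 |
| 50% | 95 | 51 | 46 | 16 |
| 70% | 100 | 79 | 79 | 30 |

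Here the multi-gas median was left on its raw scale with half the variance of the first gas, so single-gas patients carry more weight than their head count. At a 20% share and equal mortality, *w* = 0.2 / (0.2 + 0.5 × 0.8) = 0.33, and exp(0.33 × ln 0.80) = 0.93, which matches the simulated pooled OR of 0.93. Restricted to patients with two or more gases, the same analysis was significant in about 1% to 5% of replicates (nominal 2.5%).

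**The case against.** The strongest reply is that the whole-cohort comparison answers a legitimate question. The primary result belongs to the whole cohort, drawn as a "Retrospective census of all eligible patients meeting inclusion/exclusion criteria". For a single-gas patient the result truly does not depend on which gas is chosen. Asking whether the exposures agree where they can differ is a different question. This stands: the planned comparison is incomplete, not invalid.

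A reader might also infer that the plan will declare a fragile result robust. The documents do not support that. They set no robustness rule, and the significance criterion in 6.2 is attached to the primary model. The significance percentages above apply only if someone carries that criterion over to 6.3. Because ORs with intervals must be reported, the shrinkage would often be visible: in the extreme case with equal mortality, 1.22 against 1.04 to 1.06 at shares of 20% to 30%, and about half the log OR lost at 50%.

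The extreme case is also hard to reach. With correlation 0.75, marginal log ORs of 0.20 and 0 imply a mutually adjusted first-gas log OR of 0.20 / (1 − 0.75²) = 0.457 (OR 1.58) and a median log OR of −0.75 × 0.457 = −0.343 (OR 0.71), so the median must act in the opposite direction. Equal mortality is likewise a choice; if single-gas patients die less often, the dilution is weaker.

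Finally, having two or more gases is determined after the first. Patients who die or leave before a second gas are removed, and the median in those who remain includes later gases that may reflect deterioration. A reader might infer that the multi-gas subset should settle the matter alone; this selection is the reason it should not. What it does offer is a contrast in which both models are fitted to the same patients, so case mix does not differ between the two fits.

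**Conclusion.** The point holds as a minor one. The identity is arithmetic, the eligibility rule admits the patients it affects, and the plan does not ask for the counts needed to judge the dilution. Its direction is certain and its size is not. Over assumed shares of 20% to 70%, a true median OR of 1.00 in multi-gas patients would appear as about 1.04 to 1.15 with equal mortality, or about 1.01 to 1.10 with 4% and 12%. If only the first gas matters, the distortion is about 0.01 to 0.05.

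These figures rest on an assumed share, effect size, correlation and mortality, and on models without the planned covariates. They show what could happen, not what will. The primary estimate is unaffected. The same identity applies to the peak-value variant in section 5.

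**What to change.** Add to 6.3:

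> Report the number of ABGs per patient, and the number of patients and deaths with exactly one ABG. Alongside the whole-cohort analysis, fit the first-ABG and median-ABG models in the same patients with two or more ABGs, and report the change in OR with its 95% CI from both comparisons when describing robustness to the choice of ABG.

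Because the two fits in each comparison share patients, the interval for the change should allow for that pairing, for example by resampling patients. Both ORs should be expressed per the same unit of the ratio.

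The cost is one SAP addition, two extra model fits and no new data, since computing a median already requires all the gases. Intervals in the subset will be wider. Because membership is determined after the first gas, the subset informs only the first-versus-median contrast and does not replace the primary or whole-cohort estimate.

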6.1 Descriptive Analysis

- Continuous variables: mean \pm SD or median (IQR)

- Categorical variables: counts and percentages
- Compare baseline characteristics across $\text{PaO}_2/\text{PaCO}_2$ quartiles using ANOVA/Kruskal-Wallis for continuous variables and chi-square/Fisher's exact test for categorical variables

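### The only analysis named for ICU length of stay is an optional Cox model with death as the event, which estimates the hazard of ICU death and not length of stay

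*Combined protocol and SAP*

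**What the plan says.** Section 2 gives as its first secondary objective an exploration of the relation between PaO2/PaCO2 "ratio categories (e.g., tertiles or quartiles) and ICU length of stay".

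The rest of the plan does little with that objective:

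- Section 4 requires "Documented ICU discharge status" for inclusion, but no discharge time. It also requires at least one arterial blood gas (ABG).
- Section 5 names one outcome, binary ICU mortality. It gives length of stay no start, end, unit or rule for patients who die. The primary exposure comes from the first ABG of the stay.
- Section 6.1 sets general summary formats. Its one instruction to compare groups reads "Compare baseline characteristics across" the ratio quartiles, and length of stay is not a baseline characteristic.
- Section 6.2 models ICU mortality only.
- Section 6.3 names length of stay once, in a line marked optional: "Cox proportional hazards for ICU length of stay, treating death as event". Nothing there or elsewhere says how live discharge is handled.
- Section 8 asks for regression results in general and odds ratios in particular, and names no length-of-stay result.

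**The concern.** A patient leaves the ICU either alive or dead, and length of stay depends on the rates of both exits. A Cox model with death as its event, and live discharge censored in the usual way, uses only the death rate. It describes how the ratio relates to dying in the ICU, which the primary analysis already addresses on another scale, and leaves the discharge rate unexamined.

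Two things are at stake. Because the line is optional and nothing else is committed, the first secondary objective may go unanswered. If the line is run, a hazard ratio for death may be reported as a length-of-stay finding.

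**Working it through.** The plan gives no sample size, mortality, discharge rate or length-of-stay figure, so there is no figure of its own to reproduce. All hazards below are assumed, constant per day, and show only what is possible.

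**Formulas.** Let d be the hazard of ICU death and c the hazard of live discharge.

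- Mean stay = 1/(d + c)
- ICU mortality = d/(d + c), so the odds of ICU death = d/c
- Death hazard ratio (HR), discharge censored = d2/d1
- Any-exit HR = (d2 + c2)/(d1 + c1)

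**Step 1. No death effect, large difference in stay.** Take d = 0.02 in both groups and c = 0.10 versus 0.20.

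- Death HR = 0.02/0.02 = 1.0
- Mean stay = 1/0.12 = 8.33 versus 1/0.22 = 4.55 days
- Odds of ICU death = 0.02/0.10 = 0.20 versus 0.02/0.20 = 0.10, a crude odds ratio of 0.5. Even as a mortality analysis, then, the Cox line asks a different question from the primary model.

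**Step 2. Range.** Keep the death HR at 1.0, vary d from 0.01 to 0.04 and the discharge hazard ratio from 1.25 to 2.0.

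| Reference c | Smallest difference in mean stay (days) | Largest difference (days) |
|---|---|---|
| 0.10 | 1/0.14 − 1/0.165 = 1.08 | 1/0.11 − 1/0.21 = 4.33 |
| 0.20 | 1/0.24 − 1/0.29 = 0.72 | 1/0.21 − 1/0.41 = 2.32 |

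**Step 3. Direction is not fixed either.** Take a death HR of 2.0 (d = 0.02 versus 0.04) with reference c = 0.20, so reference stay is 1/0.22 = 4.55 days. A second group with c = 0.10, 0.18 or 0.30 has a mean stay of 1/0.14 = 7.14, 1/0.22 = 4.55 or 1/0.34 = 2.94 days: longer, equal or shorter.

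**Step 4. If any ICU exit were the event.** The pair in step 1 gives an exit HR of 0.22/0.12 = 1.83, and those in step 3 give 0.14/0.22 = 0.64, 0.22/0.22 = 1.00 and 0.34/0.22 = 1.55. Total stay is tracked. The two kinds of exit are merged, however. Against d = 0.02 and c = 0.10 (mean stay 8.33 days, mortality 0.02/0.12 = 16.7%), an exit HR of 0.15/0.12 = 1.25 with mean stay 1/0.15 = 6.67 days arises from:

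- faster recovery (d = 0.02, c = 0.13), mortality 0.02/0.15 = 13.3%; or
- more deaths (d = 0.05, c = 0.10), mortality 0.05/0.15 = 33.3%.

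**Step 5. Where the clock should start.** Patients enter the cohort only if still in the ICU at their first ABG. Take two groups with no true difference (d = 0.04, c = 0.10) and exponential waits to the first ABG with means 0.25 and 1.0 day (assumed). Among those who reach the ABG, its mean time is 1/(4 + 0.14) = 0.24 versus 1/(1 + 0.14) = 0.88 days, and the mean stay after it is 1/0.14 = 7.14 days in both. Mean stay from admission is therefore 7.4 versus 8.0 days, from ABG timing alone. In a simulation of this scenario (18,438 of 20,000 patients kept), the discharge HR was 0.93 on a clock from admission, 1.01 on a clock from the ABG, and 1.01 from admission with delayed entry at the ABG.

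**The case against.** The strongest reply is that the Cox line is a legitimate cause-specific mortality model with time in the ICU as its scale. That stands. The model is valid for the hazard of ICU death, and the fault is that it is offered for length of stay.

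A second reply is that the line may mean any ICU exit, with deaths counted among the events. A reader might infer that the analysis then fails just as badly because it merges death and recovery. The documents do not support that inference. The stated objective is length of stay, not time to recovery, and step 4 shows total stay is tracked. The committed mortality model would also help tell the two step 4 scenarios apart: their crude odds ratios are (0.02/0.13)/(0.02/0.10) = 0.77 and (0.05/0.10)/(0.02/0.10) = 2.5, in opposite directions. On that reading, separating the exits is a refinement. It remains the less natural reading of a line that names death as its event.

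Third, the objective is only to explore, the summary formats in section 6.1 are not limited to baseline variables, and the general request in section 8 would cover a Cox result if one were run. All of that is fair, and a table of stay by category would partly meet the objective. The plan does not commit to one.

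Finally, the magnitudes follow from competing risks in general and do not measure harm to this cohort. That is correct.

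**Conclusion.** Wrong as written: the only analysis named for length of stay does not, on its ordinary reading, estimate length of stay. It is a second mortality analysis, compatible with a longer, equal or shorter stay. In the illustration a death HR of 1.0 goes with mean stays of 8.3 and 4.5 days, and over the grids with differences of 0.7 to 4.3 days. These figures rest on assumed constant hazards and are not predictions. The conclusion itself needs only that live discharge is censored and that discharge rates may differ between ratio categories.

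The point should be acted on, but its reach is limited. A reader might infer that the mortality findings are in doubt. They are not: the objective is secondary and exploratory, and the primary logistic analysis of ICU mortality is unaffected.

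**What to change.** 1. **Section 5.** Add a secondary outcome: ICU length of stay in days, from first ABG to live ICU discharge or ICU death. If ICU admission is preferred as the start, state that the models use delayed entry at the first ABG. Either way the defined outcome and the modelled time agree.
2. **Section 6.3.** Replace the optional line with a committed analysis by ratio category, with tertiles or quartiles chosen in advance. Fit cause-specific Cox models for live discharge and for ICU death, each censoring the other exit, and report them side by side with cumulative incidence curves for both. Adjust for the section 5 covariates. These include ventilation status, which the section 6.2 list (SpO2, "MAP, age, sex, ICU type, comorbidities") omits. As description only, report median (IQR) stay from the first ABG by category, overall and by survival status.
3. If the death-event Cox model is kept as a separate item, label it a mortality analysis with live discharge censored.
4. **Section 8.** Add the length-of-stay results.

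The cost is a few lines of SAP text, a small amount of extra analysis, and extraction of ICU admission (if used), first-ABG, and ICU discharge or death times. Sections 4 and 5 list no stay duration, so this assumes those times can be drawn from the database.
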